The primary analysis of the main secondary endpoints for efficacy will take place once all patients have completed 12 months in the study as for the primary endpoint. A further supportive set of analyses will take place following completion of 24 months in the study for all patients.

Safety endpoints

All subjects who received at least one dose of investigational products will be included in the safety analyses. Safety data will be summarized using actual treatment received, regardless of randomized treatment.

Safety and tolerability will be assessed in terms of AEs, SAEs, laboratory data and vital signs which will be collected for all subjects. AEs will be coded according to the Medical dictionary for regulatory activities (MedDRA) version 15.1 or higher. The intensity of AEs will be graded according to the NCI-CTCAE (version 4.0).

AEs, AE leading to study treatment discontinuation, AE related to study treatment, and SAEs will be listed individually by subject, and summarized by System Organ Class (SOC) and Preferred Term (PT) by treatment group. Summary of AEs with NCI-CTCAE grade 3 or 4 and most frequent PT will also be provided.

Specific attention will be given to NCI-CTCAE Grade 3 or 4 of pancreatic toxicity, Grade 3 or 4 of hepatotoxicity, allergic reactions or coagulation disorders, known to be potentially related to L-asparaginase as well as to hypoproteinemia and hyperglycemia/diabetes events.

Vital signs and laboratory data will be listed and summarized by actual treatment group based on the safety analysis set. Summary of absolute values over time (one table per vital sign/laboratory parameter) and summary of change from baseline values over time (one table per vital sign/laboratory parameter) will be presented. Patients with vital sign/laboratory values of NCI-CTCAE grade 3 or 4 will be identified.

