1. INTRODUCTION

The Statistical Analysis Plan (SAP) details the statistical methodology to be used in analyzing study data and outlines the statistical programming specifications, tables, figures and listings. It describes the planned analyses of the data collected during the study, including the safety and efficacy variables and populations, anticipated data transformations and manipulations, and other details of the analyses not provided in the study protocol, for the purpose of submission to the relevant authorities and for publication as appropriate. The results of all analyses in this SAP will be included in the Clinical Study Report (CSR).

This SAP is based on the following study documents:

- Protocol Version 7 dated 05OCT2015
- Protocol Amendment n°4 dated 05OCT2015
- Electronic Case Report Form (eCRF) for the study.

The statistical analyses will be performed in accordance with International Conference on Harmonization (ICH) E9 guidelines. This SAP conforms to the Cytel standard operating procedure STAT C002 Timing and Content of Statistical Analysis Plans.

The SAP should be validated and signed before the study database is locked.

Specifications of outputs (i.e. TLFs shells) will be described in a separate document.

The primary analyses were to be undertaken when all enrolled patients had completed treatment and follow-up period for 2 years. However, based on the outcome of the AML Advisory Board meeting conducted on 24th January 2017, there was a consensus that the study was not adequately powered for the key endpoint of overall survival (OS) and that the purpose of the statistical analyses was therefore to identify a signal strong enough to support proceeding to phase 3.

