5.8.2. Laboratory Data

5.8.2.1. Haematology, Coagulation, Biochemistry tests

Biological parameters will be described at inclusion, D1, D5, D9, D13, D18 and D23 of each course of chemotherapy. The concerned biological parameters are the followings:

- Haematology
 - Haemoglobin (g/dL)
 - Hematocrit (%)
 - Erythrocytes (T/L)
 - Leukocytes (G/L)
 - Neutrophils (G/L)
 - Blasts (%)
 - Platelets (G/L)
- Blood coagulation
 - Activated Partial Thromboplastin Time (aPTT) (sec)
 - Prothrombin time (%)
 - Fibrinogen (g/L)
 - Antithrombin III (%)
 - INR
- Blood biochemistry
 - Albumin (g/L)
 - Plasma Bicarbonate (mmol/L)
 - Creatinine clearance (mL/min)
 - Serum Creatinine
 - Glycaemia (mmol/L)
 - Alkaline Phosphatase (U/L)
 - AST (U/L)
 - ALT (U/L)
 - Cholesterol (mmol/L)
 - LDH (U/L)
 - Gamma-GT (U/L)
 - Bilirubin (μmol/L)
 - Triglycerides (g/L)
 - Sodium (mmol/L)
 - Potassium (mmol/L)
 - Calcium (mmol/L)
- Pancreas
 - Lipase (U/L)
 - Amylase (U/L)

Raw results as well as absolute and relative change from baseline will be described at each timepoint between treatment groups.

Absolute change in the biological parameter between visit V_i and baseline will be calculated according to the formula: $\text{biological parameter at } V_i - \text{biological parameter at baseline}$

Relative change in biological parameter between visit V_i and baseline will be calculated according to the formula: $\frac{\text{biological parameter at } V_i - \text{biological parameter at baseline}}{\text{biological parameter at baseline}} \times 100$

All laboratory data will be provided in data listings. A subset listing will be presented for all clinically significant abnormal laboratory values. Data will be summarized by treatment group and patients with laboratory values of NCI-CTCAE grade 3 or 4 will be identified.

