14.3.1.2.6	Incidence of Treatment Related Treatment Emergent Serious Adverse Events by Preferred Term	Safety
14.3.1.2.7	Incidence of Treatment Emergent Adverse Events of Special Interest by Preferred Term	Safety
14.3.1.2.8	Incidence of Treatment Emergent Adverse Events of Special Interest with Toxicity Grade of 3 or 4 by Preferred Term	Safety
14.3.1.2.9	Incidence of Treatment Emergent Adverse Events Occurring in at least 5% of Patients in either Treatment Group by MedDRA Preferred Term	Safety
14.3.1.3	Listing of Treatment Emergent Adverse Events Leading to Either GRASPA or Chemotherapy Withdrawal	Safety

Table/Figure Number	Output Title	Analysis Set
	Deaths	
14.3.2.1	Deaths and Deaths within 28 Days After Last IMP Administration	Safety
14.3.2.2	Listing of All Deaths	Safety
	Clinical Laboratory Data	
	Biochemistry	
14.3.3.1.1	Biochemistry – Summary of Shift From Baseline to Worst Post-Baseline Results	
14.3.3.1.2	Biochemistry – Summary Statistics for Clinically Significant Parameters by Treatment Group and Time	
	Hematology	
14.3.3.2.1	Hematology – Summary of Shift From Baseline to Worst Post-Baseline Results	Safety
14.3.3.2.2	Hematology – Summary Statistics for Clinically Significant Parameters by Treatment Group and Time	Safety
	Coagulation	
14.3.3.3.1	Coagulation – Summary of Shift From Baseline to Worst Post-Baseline Results	Safety

Table/Figure Number	Output Title	Analysis Set
14.3.3.3.2	Coagulation – Summary Statistics for Clinically Significant Parameters by Treatment Group and Time	Safety
	Other Safety Parameters	
	Vital Signs Data	
14.3.4.1.1	Vital Signs – Descriptive Statistics for Change From Baseline	Safety
14.3.4.1.2	Vital Signs – Listing of Clinically Significant Values	Safety
14.3.4.2	ECOG Performance Status – Shift From Baseline to Worst Post-Baseline Value	Safety

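### SAP 8.1 limits the only routine laboratory-by-time tables to an undefined clinically significant subset, in conflict with protocol 15.3.3 and SAP 5.8.2.1

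*SAP*

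**What the plan says.** Three places bear on how routine laboratory data are summarised over time.

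- **Protocol 15.3.3, safety endpoints.** Two summaries are promised without restriction. One gives the measured levels at each visit, with a separate table for every parameter. The other does the same for changes: "summary of change from baseline values over time (one table per vital sign/laboratory parameter) will be presented".
- **SAP 5.8.2.1.** The schedule is set first: "Biological parameters will be described at inclusion, D1, D5, D9, D13, D18 and D23 of each course of chemotherapy". A closed list follows, introduced by "The concerned biological parameters are the followings". The analysis is then stated: "Raw results as well as absolute and relative change from baseline will be described at each timepoint between treatment groups". Clinical significance appears once in this section, for a different output: "A subset listing will be presented for all clinically significant abnormal laboratory values".
- **SAP 8.1.** The by-time tables for biochemistry (14.3.3.1.2), hematology (14.3.3.2.2) and coagulation (14.3.3.3.2) share one title: "Summary Statistics for Clinically Significant Parameters by Treatment Group and Time".

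The SAP introduction adds that "Specifications of outputs (i.e. TLFs shells) will be described in a separate document". That document is not among those available. SAP section 6, on changes to planned analyses, covers the PFS definition, the change of primary endpoint and the dropped interim analysis. It does not mention laboratory outputs.

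**The concern.** The table list is what a programming team builds from, and here it is narrower than both the protocol and the SAP's own method section. The narrowing rests on a term that neither document defines for choosing parameters. A reader of the study report could not tell whether a parameter is absent because it was never on a pre-chosen list or because someone left it out after seeing the data.

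The by-time view matters in this design. Cytarabine is given on Days 1 to 10 and GRASPA on Day 11 (protocol 8.4). Of the scheduled laboratory days, D9 falls just before the infusion and D13, D18 and D23 fall after it. A by-arm summary at those days shows whether a parameter moves after the infusion and whether it recovers before the next course. Protocol 15.3.3 gives specific attention to coagulation, hepatic and pancreatic toxicity, and much of that shows first in laboratory values.

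**Working it through.** No figure in the plan needs reproducing. The check is a count and a comparison of texts.

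**1. Parameters in SAP 5.8.2.1.** Haematology 7, coagulation 5, biochemistry 16, pancreas 2: 7 + 5 + 16 + 2 = 30.

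**2. What each text delivers over time**

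| Source | Parameters covered | Content |
|---|---|---|
| Protocol 15.3.3 | every laboratory parameter | absolute values; change from baseline |
| SAP 5.8.2.1 | all 30 listed | raw values; absolute and relative change |
| SAP 8.1, three by-time outputs | unspecified subset | summary statistics |

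Read literally, the protocol asks for 2 × 30 = 60 tables and SAP 8.1 has 3 titles. That gap is not the defect, because one title can cover many parameters. The defect is the restriction in the title.

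**3. Is the subset defined?** No. For laboratory data, the SAP text uses the phrase only for the listing of abnormal values. For vital signs, 8.1 uses it for a listing of values (14.3.4.1.2), while the change-from-baseline table (14.3.4.1.1) has no filter. Elsewhere, then, the phrase describes observed values rather than a named set of parameters.

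**4. Does another listed output fill the gap?**

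- The shift tables (14.3.3.1.1, 14.3.3.2.1, 14.3.3.3.1) carry no filter, but they report the worst post-baseline value. They do not separate the days before the infusion from the days after it.
- Grade 3-4 identification and the listing of abnormal values pick out patients and values. They give no time course by arm.
- Adverse event tables depend on reporting. Under protocol 11.1.2.1 an investigator may leave out an abnormal value that is scheduled, without symptoms, judged not medically significant and without effect on treatment.
- By-subject listings contain the timing but do not summarise it.

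**5. Where do lipase and amylase go?** SAP 5.8.2.1 puts them under their own pancreas heading. SAP 8.1 has only biochemistry, hematology and coagulation, so the list does not say which by-time table would carry them.

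**The case against.** The strongest reply is that 5.8.2.1 is the governing text and already requires the full description, while 8.1 is only a list of short titles. The list is incomplete elsewhere too: the physical-examination shifts in SAP 5.8.3.1 have no table there, and the vital-sign table is titled for change only although 5.8.3 also asks for raw results. On this view a loose title does not override the method. That stands as a reason to rate the point modestly. It does not remove the conflict, because these titles do not merely omit content; they state a restriction that contradicts the method section.

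A reader might infer that the subset must be picked from results by arm. The documents do not support that. The shells are separate and could name the parameters in advance, and the SAP is to be signed before database lock. Both documents already name areas of safety interest, so parameters of clinical interest chosen beforehand is a plausible meaning. Open label does not mean that aggregated laboratory data were consulted. What stands is narrower: the plan does not rule out a data-driven choice, and even a pre-chosen subset would depart from protocol 15.3.3 without being recorded.

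A reader might also want to size the problem as the number of parameters expected to differ between arms by chance. That does not fit. No significance tests on laboratory parameters are planned, the phrase refers to clinical significance, and many of the 30 are strongly related (haemoglobin with hematocrit, AST with ALT, prothrombin time with INR).

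Nor do the rates in the ALL trial (protocol Table 2: antithrombin III decrease 11.5% v 71.4%, hypofibrinogenemia 26.9% v 64.3%) measure the loss. They are adverse event rates for GRASPA against native asparaginase, with GRASPA lower, whereas the control here receives no asparaginase. They show only that these parameters are relevant.

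Finally, much safety information remains: special-interest event tables (14.3.1.2.7 and 14.3.1.2.8), the diabetogenic and pancreatic event table in 5.8.1, unfiltered shifts and full listings. Timing could be read from the listings, though less conveniently. A class effect would therefore not simply vanish from the report.

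**Conclusion.** The conflict holds on the text. The three routine laboratory-by-time outputs cover an undefined part of 30 parameters that the protocol and SAP 5.8.2.1 both require in full, and section 6 does not record the reduction. How many parameters would be lost cannot be stated, because the subset is not named. Nothing in 8.1 guarantees a by-time summary for antithrombin III, fibrinogen, lipase or amylase.

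The conclusion assumes that the outputs are built as titled. If the shells cover all 30 parameters, only the titles are wrong. If they name a subset in advance, the concern about selection falls away but the unrecorded departure from the protocol remains.

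The effect is confined to safety reporting. The correction should be made before database lock.

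**What to change.** In SAP 8.1, delete the words restricting 14.3.3.1.2, 14.3.3.2.2 and 14.3.3.3.2 to clinically significant parameters. Replace them with: *for all parameters listed in 5.8.2.1 (with lipase and amylase under biochemistry): absolute values and change from baseline*. Keep clinical significance only for the subset listing of abnormal values, and align the shells.

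If the sponsor prefers a subset, it should name the parameters before database lock and record the reduction in section 6 as a departure from protocol 15.3.3. This is the weaker option, since it gives up summaries that the protocol promises.

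The main change costs SAP wording and additional table pages from the same program. It needs no new data.

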8.2. Data Listings to be Generated

	Subject Data Listings	
	Subjects Disposition	
16.2.1.1	Patient Disposition and Analysis Sets	ITT
16.2.1.2	Subject Visit Dates	ITT

Protocol Deviations		
16.2.2.1	Deviations Relating to Inclusion/Exclusion Criteria	All Patients
16.2.2.2	Other Protocol Deviations	ITT
Demographic Data and Baseline Characteristics		
16.2.4.1	Demographic Data	ITT
16.2.4.2	Baseline Characteristics	ITT
16.2.4.3	Medical and Surgical History	ITT
16.2.4.3.1	Medical History Related to Primary Disease Condition	ITT
16.2.4.3.2	Medical History Related to Other Disease	ITT
16.2.4.3.3	Physical Examination	ITT
Previous and Concomitant Medications		
16.2.4.4.1	Prior Medications	ITT
16.2.4.4.2	Concomitant Medications	ITT
Compliance and/or Drug Concentration Data		
Drug Exposure		
16.2.5.1.1	GRASPA Administration	Safety

16.2.5.1.2	Cytarabine Administration	Safety
	Efficacy Data	
16.2.6.1	Tumour Lesions Measurements	ITT
16.2.6.2	Tumour Assessment Responses – Investigator and Central Readings	ITT
16.2.6.3	PFS and Overall Survival – Time-to-Event Variables	ITT
16.2.6.4	PK and PD Parameters	Safety
16.2.6.5	Biomarker Parameters	Safety
16.2.6.6	Immunogenicity Parameters	Safety
16.2.6.7	Quality of Life – QLQ-C30	ITT
	Adverse Event Listings	
16.2.7.1	Treatment Emergent Adverse Events	Safety
	Clinical Laboratory Data	
16.2.8.1	Biochemistry Data (SI Units)	Safety
16.2.8.2	Hematology Data (SI Units)	Safety
16.2.8.3	Coagulation Data (SI Units)	Safety

Other Safety Parameters		
16.2.9	Vital Signs Parameters and Weight Assessments	Safety
